## **17.0 SERIOUS ADVERSE EVENTS (SAE)**

### **17.1 Definition**

A serious adverse event is defined as per the Code of Federal Regulation Title 21 Part 312

<http://www.accessdata.fda.gov/scripts/cdrh/cfdocs/cfcfr/cfrsearch.cfm?fr=312.32>

### **17.2 Reporting SAEs**

Any serious and adverse event due to any cause, which occurs during the course of the investigation (i.e. any time after informed consent, regardless of study drug exposure), will be reported to the PI and study physician within 24 hours of learning of the event. All serious adverse events will be reported to the Wake Forest IRB within 7 days of study personnel learning of the event.

### **17.3 IND Safety Reporting**

As the Sponsor of the IND related to this study, any unexpected fatal or life-threatening suspected adverse reactions will be reported to the FDA no later than 7 calendar days after the initial receipt of the information per 21 CFR 312.32(c)(2).

Reporting of any (1) serious, unexpected suspected adverse reactions (2) findings from other clinical, animal, or in-vitro studies that suggest significant human risk, and (3) a clinically important increase in the rate of a serious suspected adverse reaction no later than 15 calendar days after determining that the information qualifies for reporting per 21 CFR 312.32(c)(1).

## **18.0 ETHICS & REGULATORY CONSIDERATIONS**

### **18.1 Ethical Standard**

Study investigators are charged with conducting this study in full conformity with:

1. Good Clinical Practice (GCP) guidelines, as defined by the International Conference on Harmonisation (ICH) Guideline, Topic E6
2. The United States Code of Federal Regulations, Title 21, Part 50 (21CFR50) – Protection of Human Subjects
3. 21CFR56 – Institutional Review Boards (IRBs)
4. HIPAA
5. State and Federal regulations and all other applicable local regulatory requirements and laws.

Study personnel involved in conducting this study will be qualified by education, training and experience to perform their respective task(s) in accordance with GCP.

## **18.2      Institutional Review Board (IRB)**

This protocol and the associated informed consent documents and recruitment material will be approved by the Wake Forest IRB which is registered with the Office for Human Research Protections (OHRP). Any amendments to the protocol or consent materials must also be approved before they are placed into use. The investigator shall notify the IRB of deviations from the protocol or serious adverse events occurring at the site, in accordance with local procedures.

## **18.3      Informed Consent & HIPAA Authorization**

In obtaining and documenting informed consent, the investigator should comply with the applicable regulatory requirement(s), and should adhere to GCP and to the ethical principles that have their origin in the Declaration of Helsinki. Prior to the beginning of the trial, the investigator should have the IRB's written approval of the written informed consent form (ICF) and any other written information to be provided to participants. Participants, their relatives, guardians, or authorized representatives and study partners will be given ample opportunity to inquire about the details of the study. Prior to a subject's participation in the trial, the written informed consent form and HIPAA Authorization should be signed and personally dated by the subject and/or the subject's legally authorized representative, the study partner and by the person who conducted the informed consent discussion. Participants should be provided a copy of the signed ICF.

The informed consent will not only cover consent for the trial itself, but for the genetic research, biomarker studies and biological sample storage. The consent for storage will include consent to access stored data and biological samples for secondary analyses. Consent forms will specify that DNA and biomarker samples are for research purposes only; the tests on the DNA and biomarker samples are not diagnostic in nature and participants will never receive results.

## **18.4      Participant Confidentiality | HIPAA**

Participant confidentiality is strictly held in trust by the participating investigators, research staff, and the sponsoring institution and their agents. This confidentiality is extended to cover testing of biological samples and genetic tests in addition to the clinical information relating to participants. The study protocol, documentation, data and all other information generated will be held in strict confidence. No information concerning the study or the data will be released to any unauthorized third party, without prior written approval. Any data, specimens, forms, reports, and other records that leave the site will be identified only by a subject identification number to maintain confidentiality. All records will be kept in a locked file cabinet. All computer entry and networking programs will be done using subject IDs only. Information will not be released without written permission of the subject, except as necessary for monitoring by the IRB, FDA, NIA, and the OHRP.

Information about subjects will be kept confidential and managed according to the requirements of the Health Insurance Portability and Accountability Act of 1996 (HIPAA). Those regulations require a signed HIPAA Authorization informing the subject of the following:

- What protected health information (PHI) will be collected from participants in this study
- Who will have access to that information and why
- Who will use or disclose that information
- The rights of a research participant to revoke their authorization for use of their PHI.

In the event that a subject revokes authorization to collect or use PHI, the investigator, by regulation, retains the ability to use all information collected prior to the revocation of subject authorization. Each site PI, under the guidance of his/her IRB, is responsible for ensuring that all applicable HIPAA regulations and State laws are met.

## **19.0 GENETIC RESEARCH & STORAGE OF GENETIC MATERIAL**

The DNA is banked in locked freezers in the ADRC Biomarker Service. Sample tubes are bar-coded and linked to participant ID number only and banked without personal identifiers.

Only DNA from consenting participants will be banked and used to facilitate future research on aging and dementia, particularly in the discovery of genetic polymorphisms that may influence risk of developing AD. Collection of DNA will permit investigators to probe candidate genetic polymorphisms as predictors of outcome in future studies. The samples will be stored by the ADRC.

### **19.1 Storage of Biospecimen Samples**

All biospecimens being banked for future AD biomarker research will be stored by the ADRC Biomarker Service. Participant will be asked to consent to allow samples to be used for future research.

## **20.0 RISKS AND BENEFITS ASSOCIATED WITH THIS STUDY**

### **20.1 Potential Benefits of the Proposed Research to Human Subjects**

There is an urgent need to identify promising treatments for patients with AD and its prodrome aMCI. In a previous trial (Craft, Baker et al. 2012), intranasal insulin safely improved delayed memory and function in these patients. In a recent trial, these results were replicated with the subgroup of participants who used the ViaNase device, but not with the POD cohort. The proposed trial is designed to answer the important question of whether the Aptar CPS device is effective in delivering intranasal insulin into the CNS. This knowledge will enable the conduct of future Phase III trials of intranasal insulin.

There are no significant potential clinical benefits for the participants in this study. Rather, there is a clear scientific benefit for the field as a whole. The relatively minor risks posed by the intranasal administration, cognitive testing, and LP are outweighed by the value of the scientific investigations outlined in this study.

### **20.2 Inclusion of Women and Minorities**

There are currently no studies that definitively support or negate the existence of significant differences in response to intranasal insulin in subgroups defined by gender or ethnic background. A specific goal percentage for women and minority enrollment is not set for this study. However, we will monitor minority enrollment throughout the study and make special effort to encourage minority enrollment. Minority enrollment will be facilitated through minority outreach effort coordinated by the Recruitment Core at the ADRC. No participant will be excluded due to his or her sex, race, or ethnic group.

### **20.3 Inclusion of Children as Participants in Research Involving Human Subjects**

Children will not be included.

### **20.4 Data and Safety Monitoring Plan**

The principal investigator and study clinician(s) will be responsible for the overall monitoring of the data and safety of study participants, with assistance by members of the study staff. Participants will be screened at the beginning of the study and will be monitored carefully at each study visit. Participants will be queried for serious adverse events (SAEs) and selected AEs (those temporally related to study procedures) at each study visit. All SAEs and selected AEs will be recorded on an AE case report form. Based on the nature of the AE, study clinicians will determine the severity of the event and association with the study. All serious adverse events will be reported. Serious adverse events are defined as events that are (1) life-threatening or fatal, (2) result in severe or permanent disability, or (3) require hospitalization. SAEs will be reported to the IRB within 7 days of investigator

knowledge of the event if they are related and unanticipated (i.e. if they qualify as an unanticipated problem). All serious adverse events will be followed until resolution, or 90 days after study participation has been terminated.

"Severity" of events will be graded according to the following guidelines:

1. Mild: The participant is aware of, but can easily tolerate, the event
2. Moderate: The discomfort of the event is severe enough to interfere with some usual activities
3. Severe: The participant is incapacitated, and unable to perform most or all usual activities

The "study-relatedness" will be assigned according to the following guidelines:

1. Definitely Related: The reaction follows a reasonable temporal sequence and is known to be an effect of participation or a procedure
2. Possibly Related: The reaction follows a reasonable temporal sequence, and current medical knowledge does not preclude a relationship between participation or procedure and the event.
3. Unlikely: Little evidence to suggest a causal relationship (e.g. the event did not occur within a reasonable time after administration of the trial medication) or another reasonable explanation for the event (e.g. another clinical condition or other concomitant treatment).
4. Definitely Unrelated: Current medical knowledge precludes a causal relationship between participation or procedure and the event or the cause of the reaction is known to be other than participation or procedure.

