LDH	LACTATE DEHYDROGENASE
LP	LUMBAR PUNCTURE
LTP	LONG TERM POTENTIATION
MCV	MEAN CORPUSCULAR VOLUME
ML	MILLILITER
MMA	METHYLMALONIC ACID
MMSE	MINI MENTAL STATE EXAMINATION
MPRAGE	MAGNETIZATION PREPARED RAPID GRADIENT ECHO
MR/MRI	MAGNETIC RESONANCE / MAGNETIC RESONANCE IMAGING

NBAC	NATIONAL BIOETHICS ADVISORY COMMISSION
NIA	NATIONAL INSTITUTE ON AGING
NIH	NATIONAL INSTITUTES OF HEALTH
NINCDS/ADRDA	NATIONAL INSTITUTE OF NEUROLOGICAL AND COMMUNICATIVE DISEASES AND STROKE / ALZHEIMER'S DISEASE AND RELATED DISORDERS ASSOCIATION
NBDA	N-METHYL – D-ASPARTATE
NSAID	NON-STEROIDAL ANTI-INFLAMMATORY DRUGS
OHRP	OFFICE FOR HUMAN RESEARCH PROTECTIONS
PBMC	PERIPHERAL BLOOD MONONUCLEAR CELL
PD	PROJECT DIRECTOR
PCP	PRIMARY CARE PHYSICIAN
PET	POSITRON EMISSION TOMOGRAPHY
PHI	PROTECTED HEALTH INFORMATION
PI	PRINCIPAL INVESTIGATOR
PID	PARTICIPANT ID
RBC	RED BLOOD CELL
RE	RANDOM EFFECTS
ROI	REGIONS OF INTEREST
SAE	SEVERE ADVERSE EVENT
SD	STANDARD DEVIATION
SGOT	SERUM GLUTAMIC OXALOACETIC TRANSAMINASE
SGPT	SERUM GLUTAMIC PYRUVIC TRANSAMINASE
T	TESLA
TSH	THYROID STIMULATING HORMONE
U/A	URINALYSIS
WBC	WHITE BLOOD COUNT

TITLE	Study of Nasal Insulin to Fight Forgetfulness "SNIFF" – Combination Intranasal Insulin and Empagliflozin Trial
PROJECT DIRECTOR	[name].
STUDY SPONSOR	Wake Forest University Health Sciences (WFUHS) / Alzheimer's Disease Research Center (ADRC)
STUDY PHASE	Phase II Pilot Study
INDICATION	Preclinical AD, amnestic mild cognitive impairment (aMCI) or mild Alzheimer's disease (AD)
AIM OF STUDY	The proposed pilot study will provide safety and efficacy preliminary data regarding singular and combined effects of two therapeutic approaches, intranasal insulin and treatment with the sodium-glucose cotransporter type 2 inhibitor (SGLT2i) empagliflozin, to correct bioenergetic and vascular dysfunction in adults with preclinical AD and amnestic mild cognitive impairment (aMCI) or early AD

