PRIMARY OBJECTIVE	We will test the hypothesis that 1 month of treatment with INI (40 IU q.i.d.), with the SGLT2i empagliflozin (empa; 10 mg q.d.), and with combined insulin plus empagliflozin (INI+empa) will result in safety profiles (number of treatment-related serious adverse events/primary outcome) that are similar to placebo.
SECONDARY OBJECTIVES	We will determine the effects of singular and combined therapy on AD cerebrospinal fluid biomarkers, cerebral blood flow (CBF) and cognition.
PRIMARY OUTCOME MEASURE	Number of treatment-related serious adverse events
SECONDARY OUTCOME MEASURES	PACC5, ADAS-Cog14, CSF A $\beta$ 40, A $\beta$ 42, total tau, and phospho-tau 181, whole brain CBF
STUDY DESIGN	Single-site, double-blind study
SAMPLE SIZE	n=60
SUMMARY OF KEY ELIGIBILITY CRITERIA	
 
Cognitively normal with positive amyloid (amyloid PET SUVR>1.21, CSF A<math>\beta</math>42<600 pg/ml)
 
Diagnosis of amnestic mild cognitive impairment (MCI) or early AD (CDR 0.5 or 1, MMSE>21)
 
Age: 55 to 85 years (inclusive)
 

DRUG DOSAGE & FORMULATION	40 International Units Humulin® R U-100 (Eli Lilly, Inc.) q.i.d.; empagliflozin (10 mg q.d.)
DURATION OF PARTICIPATION	8 weeks (4 weeks on active treatment)
PLACEBO	Insulin diluent (Eli Lilly, Inc.); cellulose capsule

ROUTE OF ADMINISTRATION	Intranasal (insulin); oral (empagliflozin)
PROCEDURES	Physical and neurological exam, nasal examination, cognitive testing, magnetic resonance imaging (MRI), continuous glucose monitoring, actigraphic sleep assessment, lumbar puncture, vitals, clinical labs, CSF and blood analysis and banking and APOE genotyping.

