### **5.2 Rationale for Primary and Secondary Outcome Measures**

Because no published study has examined the safety of empagliflozin in adults with Alzheimer's disease or in combination with intranasal insulin, the proposed study specifies safety, defined as number of treatment-related adverse events, as the primary outcome..

Regarding secondary measures, in previous studies intranasal insulin acutely improved cognitive performance and affected CSF levels of AD biomarkers as well as MRI measures of vascular integrity (Reger et al. 2008; Craft et al. 2012; Kellar et al. 2021). Thus examining effects on these measures will provide information to be used in the design of a future Phase II trial.

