### **13.5 Lumbar Puncture**

Lumbar puncture may be associated with pain during the performance of the procedure. This is usually temporary and confined to the lower back. Headache may occur in about 5% of elderly people who undergo lumbar puncture. Less commonly, in about 1-4% of participants, a persistent low-pressure headache may develop, probably due to leakage of CSF. Lower rates of post-LP headache have been noted in elderly patients, and when atraumatic (Sprotte) needles are used. If a post-LP headache persists it may need additional treatment, e.g. with fluids and analgesics. Uncommonly a blood patch (injection of some of the participant's blood to patch the CSF leak) may be needed. Potential but rare risks of lumbar puncture include infection, damage to nerves in the back, and bleeding into the CSF space. The risk of these is much less than 1%.

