## **16.0 ADVERSE EVENTS**

### **16.1 Definition**

An adverse event (AE) is defined as per the Code of Federal Regulation Title 21 Part 312.

<http://www.accessdata.fda.gov/scripts/cdrh/cfdocs/cfcfr/cfrsearch.cfm?fr=312.32>

Adverse events which occur after informed consent is signed include but are not limited to: (1) worsening or change in nature, severity, or frequency of conditions or symptoms present at the start of the study; (2) participant deterioration due to primary illness; (3) intercurrent illness; and (4) drug interaction. An abnormal laboratory value will only be reported as an AE if the investigator considers it to be an AE, or if it leads to the participant being withdrawn from the study.

The investigator should attempt to establish a diagnosis of the event based on signs, symptoms, and or other clinical information. In such cases, the diagnosis should be documented as the AE and not the individual signs or symptoms. Symptoms and conditions present at the beginning of the study will be characterized, so that AEs can be defined as any new symptom, or any increase in frequency or severity of an existing symptom.

Following questioning and evaluation, all AEs, whether determined to be related or unrelated to the study drug by a medically qualified site PI or clinician (MD, DO, NP or PA), must be documented in the participant's medical records, in accordance with the investigator's normal clinical practice, and on the AE e-CRF. Each AE is evaluated for duration, severity, seriousness, and causal relationship to the study drug.

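### The primary count of treatment-related SAEs has two unreconciled definitions of seriousness and no stated link to either causality judgement, so procedure complications could be counted

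*Combined protocol and SAP*

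**What the plan says.** **Endpoint.** The synopsis and section 1.1 give the primary outcome as "number of treatment-related serious adverse events", and section 6.0 agrees. Section 5.2 gives it as "number of treatment-related adverse events, as the primary outcome", without the word serious.

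**Serious.** Section 17.1 reads: "A serious adverse event is defined as per the Code of Federal Regulation Title 21 Part 312". It does not list the criteria. Section 20.4 reads: "Serious adverse events are defined as events that are (1) life-threatening or fatal, (2) result in severe or permanent disability, or (3) require hospitalization". It does not refer back to 17.1. The glossary expands the abbreviation SAE as "SEVERE ADVERSE EVENT".

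**Treatment-related.** Section 16.1 requires: "Each AE is evaluated for duration, severity, seriousness, and causal relationship to the study drug". It supplies no grades. Section 20.4 supplies four grades of study-relatedness. The top grade is "The reaction follows a reasonable temporal sequence and is known to be an effect of participation or a procedure". Possibly Related and Definitely Unrelated are also worded for participation or procedure. Trial medication appears only in an example under the Unlikely grade.

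**Procedures.** Sections 8.3 and 8.7 schedule a lumbar puncture (LP) at Visits 3 and 6 for every participant. Both also have 40 IU of insulin given during the LP, with no restriction by arm in the text.

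**The concern.** An event enters the primary count only if it is both serious and treatment-related. The protocol defines the first term in two places without reconciling them, and never says which of its two causality judgements decides the second. Two people applying it in good faith could report different primary results from the same events.

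The practical risk lies with procedure complications. They occur whatever the assigned drug, and the only scale available to the investigator grades them as related. The primary hypothesis is that the safety profiles of the active arms are similar to placebo. Non-drug events in all four arms would blur that comparison. With so few drug-related events expected, a single misclassified event could make up most or all of the primary result.

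**Working it through.** The protocol has no power calculation (section 12.1), so there is no derived figure to reproduce. The check has two parts.

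**Part 1: one event under each rule.** Take an LP complication in a placebo participant that requires hospital admission.

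| Question | Rule | Result |
|---|---|---|
| Serious? | 20.4 list | Yes (hospitalization) |
| Serious? | 17.1 | Depends on regulatory text that the protocol does not reproduce |
| Serious? | 5.2 wording | Not asked |
| Related? | 20.4 scale | Definitely Related |
| Related? | 16.1 | A drug judgement, with no grades to record it on |

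With the 20.4 scale the event adds 1 to the placebo count. With a study-drug judgement of unrelated it adds 0. No section says which applies, or which grades qualify.

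Two features make this harder to resolve afterwards:

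- Section 17.2 collects SAEs from consent onward regardless of drug exposure, and nothing limits the endpoint to events after treatment starts. The first LP falls at Visit 3, where study drug is first distributed, so 60 of the 120 LPs come at or before the start of home dosing.
- Insulin is given during both LPs with no stated arm restriction. On the text as it stands, drug and procedure coincide at those visits, and one combined grade cannot separate them.

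**Part 2: size.** Inputs:

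- Participants: 20 + 40 = 60 (section 6.1).
- Arms: four, equal allocation (section 15.2, Randomization), so 60/4 = 15 per arm.
- LPs: 60 × 2 = 120 in total, 15 × 2 = 30 per arm.
- Rate of infection, nerve damage or bleeding after LP: section 13.5 says only that it is far below 1%. I assume 0.1% to 0.5% per LP, independent LPs and no dropout.

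Expected events = number of LPs × p. Chance of at least one = 1 − (1 − p)^(number of LPs).

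| Assumed p per LP | Expected in 120 | At least one in 120 | At least one in an arm (30) |
|---|---|---|---|
| 0.1% | 120 × 0.001 = 0.12 | 1 − 0.999^120 = 11.3% | 1 − 0.999^30 = 3.0% |
| 0.5% | 120 × 0.005 = 0.60 | 1 − 0.995^120 = 45.2% | 1 − 0.995^30 = 14.0% |

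Given the wording of section 13.5, the lower row is the less plausible one.

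Effect of one event on one arm: 1/15 = 6.7 percentage points.

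**The case against.** The strongest reply is that section 16.1 already requires a study-drug judgement for every adverse event. The word treatment-related maps more naturally to that than to a study-relatedness scale placed in the monitoring plan next to the IRB reporting rule. This stands in part. A reader might infer that the protocol grades relation to procedures instead of to drug. It does not: both concepts are present, participation can include taking study drug, and miscounting is possible rather than prescribed. What remains is that only one concept has grades and neither is linked to the endpoint.

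Four further limits also stand:

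- A reader might infer that 20.4 leaves out events that 17.1 would capture. That needs the regulatory text, which the protocol does not reproduce. The documents show two unreconciled definitions, not a proven difference in content.
- The glossary entry is a clerical slip, not a third definition. The body of the protocol uses serious throughout, and 16.1 lists severity and seriousness separately.
- Section 13.5 also says: "Less commonly, in about 1-4% of participants, a persistent low-pressure headache may develop, probably due to leakage of CSF". At 60 participants that is 60 × 1% to 4% = 0.6 to 2.4 cases, but it is not the size of this problem. A headache counts only if it is serious, few would be, and no rate for that is given. Multiplying by 120 LPs would also misread a rate stated per participant.
- A reader might infer a bias toward finding the arms alike. All arms have the same LPs, so procedure events add the same expected number to each. The effect is noise that dilutes a drug signal, and it does not favour one arm.

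Section 3.8 reports no treatment-related SAEs in the first preliminary study. That is only a loose guide here: the study gave 20 or 40 IU daily without empagliflozin, against 4 × 40 = 160 IU daily in this trial's insulin arms.

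**Conclusion.** The point holds as a defect in how the primary endpoint is defined. Seriousness has two unreconciled definitions and is missing from section 5.2. Treatment-relatedness is undefined, and the only graded scale would class a serious LP complication as Definitely Related in any arm.

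The expected number of such events is small: about 0.12 to 0.60 in the whole trial, with an 11% to 45% chance of at least one, under assumed rates of 0.1% to 0.5% per LP. The consequence of each is not small, because one event moves an arm of about 15 by 6.7 points. It should be settled before data are collected. Causality judgements that were not recorded prospectively are hard to reconstruct without bias once allocation is known.

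**What to change.** 1. Use one SAE definition: replace the list in 20.4 with a pointer to 17.1. Bring section 5.2 into line with the synopsis, section 1.1 and section 6.0. Correct the glossary entry to serious.
2. On the adverse event form, record two judgements per event with the existing four grades: relation to study drug, and relation to a study procedure.
3. State in section 12.0 that the primary outcome counts SAEs by the study-drug judgement, and name the grades that qualify. Tabulate procedure-related SAEs separately by arm.
4. Reconcile the insulin given during both LPs (sections 8.3 and 8.7) with the arm assignments in sections 6.0 and 15.2 (Randomization), so that drug and procedure causes can be told apart at those visits.

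The cost is protocol wording and one extra form field, with no new visits or staff. The downside is that the investigator makes two causality judgements per event instead of one.
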